6.1.2 ADVERSE DEVICE EFFECT (ADE)

An ADE is any untoward or unintended effect, event, or response surrounding and with a causal relationship with the use of a medical device. This definition may include any event resulting from insufficiencies or inadequacies in the instructions for use or the deployment of the device or other device malfunctions. This definition includes any event that is a result of a user error and any event that affects a user of the device (i.e. caregiver, bystander, etc).

6.1.3 UNANTICIPATED ADVERSE DEVICE EFFECT (UADE)

A UADE is any ADE, which is unanticipated and poses a risk to health or safety, or any life-threatening problem or death caused by or associated with a device, if that effect, problem, or death was not previously identified in nature, severity or degree of incidence (see Investigator Brochure [IB]). UADEs also include any unanticipated sight-threatening events and any other unanticipated serious problem associated with a device that relates to the rights, safety, or welfare of subjects.

CLARVISTA MEDICAL

PROTOCOL CP-00001 Rev.05

6.1.4 DEVICE DEFICIENCIES (DD)

A Device Deficiency (DD) is a failure of the device to meet its performance specifications or expectations, or otherwise not perform as intended. This can include either a malfunction or damage to the device or any part thereof, regardless of the source of malfunction or damage, including user error, and regardless of the presence of injury (or lack thereof) to subject, user, or bystander.

6.2 AE EVALUATION

AEs experienced in this study may be associated with the study device (i.e. ADE) or the study protocol as demonstrated in the following non-exhaustive list of examples:

Study Device (ADE)

- IOL dislocation
- Explant due to haptic break/damage
- Explant due to base and/or optic damage

Study Protocol

- Allergic reaction to dilating drops
- Lens remnants following surgery
- Capsular tear during surgery to implant study device

6.2.1 EVALUATION

All AEs will be evaluated for and by the following criteria:

- Classification (SAE, AE, ADE or combination)
- Diagnosis (or description if ADE)
- Severity
- Relationship (Causality) to study protocol or device
- Outcome
- Treatment or action taken

6.2.1.1 CLASSIFICATION

When evaluating AEs, the Investigator must determine if the event is serious using the following guidelines:

A Serious Adverse Event (SAE) is any AE (ocular or non-ocular) that:

- results in death
- results in serious injury, defined as:
 - ◆ life-threatening
 - ◆ permanent impairment of a body function (e.g. blindness) or structure
 - ◆ necessitates medical or surgical intervention to prevent permanent impairment of a body function or permanent damage to a body structure, or
 - ◆ results in a potentially sight-threatening condition

CLARVISTA MEDICAL

PROTOCOL CP-00001 Rev.05

- is a malfunction that might cause or contribute to a serious injury or death if it were to recur
- requires in-patient hospitalization or prolongation of existing hospitalization*, or
- leads to fetal distress, fetal health, a congenital abnormality, or birth defect

* Hospitalization is a criterion for assessment of seriousness. Hospitalization in the absence of a medical AE is not in itself an AE. For example, the following reports of hospitalization without a medical AE should not be considered either serious or an AE:

- admission for treatment of a pre-existing condition not associated with the development of a new AE or with worsening of the pre-existing condition (e.g. for work-up of persistent pretreatment lab abnormality)
- social admission (e.g. subject has no place to sleep)
- administrative admission (e.g. for yearly physical exam)
- optional admission not associated with a worsening of a pre-existing condition (e.g. elective cosmetic surgery or elective surgery for pre-existing repair of the Achilles tendon [which had not worsened while on study])
- hospitalization for admission without a medical AE

NOTE: For the purposes of this protocol, any UADE will be considered an SAE.

6.2.1.2 *DIAGNOSIS OR DESCRIPTION*

In all instances, it is preferable to report all AEs and SAEs by diagnosis rather than a sign or symptom if possible. This may necessitate the revision of a previously reported AE or SAE as more information is obtained.

6.2.1.3 *SEVERITY*

When evaluating AEs, the Investigator must determine the severity of symptoms using the following guidelines:

- **Mild:** Subject awareness of a sign or symptom that is easily tolerated, requires no treatment, and does not interfere with the subject's daily activities
- **Moderate:** Subject awareness of a sign or symptom which may be a low level of concern to the subject and may interfere with daily activities, but can be relieved by simple therapeutic care
- **Severe:** A sign or symptom that interrupts the subject's daily activity and requires systemic therapy or other treatment

6.2.1.4 *RELATIONSHIP (CAUSALITY) TO STUDY DEVICE OR STUDY PROTOCOL*

When evaluating AEs, the Investigator must evaluate the relationship of the event to the study device and study protocol, using the following guidelines:

- **Not Related:** AEs which are clearly and incontrovertibly due to causes other than the study device or study protocol (e.g. concomitant disease, etc)
- **Related:** AEs which are felt with a reasonable degree of certainty to be related to the study device or study protocol

CLARVISTA MEDICAL

PROTOCOL CP-00001 Rev.05

- Unknown: Adverse events for which a connection with the study device or study protocol cannot be ruled-out with certainty, or not enough information is available to assess the relationship

6.2.1.5 OUTCOME

The clinical outcome of an AE will be categorized as follows:

- Resolved without sequelae
- Resolved with sequelae (specify)
- Ongoing (i.e. continuing at time of study discontinuation)
- Death

6.2.1.6 TREATMENT OR ACTION TAKEN

Treatment or Action Taken will be categorized as follows:

- None
- Medical Intervention (specify on Concomitant Medication Source and eCRF)
- Surgical Intervention (specify on Concomitant Procedure Source and eCRF)
- Other (specify)

6.3 REPORTING

6.3.1 ON-SITE EXPEDITED REPORTING

The Investigator is obligated to report the following to the Sponsor within 24 hours of becoming aware of the event to ensure the safety of all participants in the study and to meet regulatory reporting requirements:

- All SAEs, regardless of relationship to study device or study protocol utilizing the SAE/ADE Report Form
- All AEs determined to be related to the study device (ADEs or UADEs) utilizing the SAE/ADE Report Form
- All HMIOL explants (consult Medical Monitor listed on Protocol Contacts page prior to explant, if possible)
- All Device Deficiencies (DD) utilizing the DD Report Form

Refer to the Protocol Contacts page for appropriate Sponsor contact to report the above events.

NOTE: Any explanted HMIOL devices, exchanged HMIOL optics, or any components of the HMIOL System presenting a deficiency or malfunction are to be retained by the site until collected by the Sponsor. Under no circumstances are they to be destroyed or otherwise discarded.

When reporting these events to the Sponsor, the site should forward any supporting documents along with the appropriate reporting form and complete the corresponding eCRF, if applicable. Sites must also report applicable events to the reviewing IRB/EC per its established reporting procedures.

6.3.2 OFF-SITE SAE REPORTING

As a multicenter clinical trial, the Investigators may receive "off-site" reports (e.g. an SAE Report). These are Sponsor reports of SAEs which occurred at other sites for the same trial, or in different trials using the same test article, that met the criteria for reporting. These should be reported to the reviewing IRB per their established reporting procedures.

CLARVISTA MEDICAL

PROTOCOL CP-00001 Rev.05

6.3.3 REPORTING OF COMPLAINTS FOR ANCILLARY MARKETED PRODUCTS

Any complaints, malfunctions or similar events related to ancillary marketed products used in this study should be reported by the Investigators in accordance with the reference information provided on the associated commercial packaging.

6.3.4 ADVERSE EVENTS AND SERIOUS ADVERSE EVENTS AT SUBJECT EXIT

Ongoing SAEs and ADEs will be followed until resolution or no further change in the condition is expected. Non-serious AEs that are ongoing at study exit visit or upon discontinuation from the study will be followed per the Investigator's standard of care. Documentation in the eCRF of this follow-up is not required although subject care should continue as appropriate.

6.4 SAFETY MONITORING AND REVIEW

All reported AEs will be reviewed on a weekly basis and assessed for trending and causality to study device or procedure. ADEs, UADEs, DDs, and SAEs will be reviewed upon receipt of expedited reporting (Section 6.3.1). Any unexpected trends or events will necessitate careful review and assessment of any change in the risks associated with participation or study continuation.

If an event occurs affecting a subject's risk of participation, Off-Site Reporting (Section 6.3.2) will be utilized to update sites and the IRB(s) / EC(s). If the safety profile of the event provides for the continuation of the study, Informed Consent Forms will be revised as necessary to ensure subjects' consent to continue participation given the known revised risks.

As outlined in Section 4.7.1, the Sponsor reserves the right to discontinue enrollment at any time.

7.0 CLINICAL ENDPOINTS

7.1 SAFETY ENDPOINTS

Safety will be evaluated by assessing the following:

All HMIOL Eyes Cohort:

- [REDACTED]
- [REDACTED]
- [REDACTED]
- AE rates as compared to ISO 11979-7:2014 Annex B SPE tables
- [REDACTED]
- SSI

HMIOL Cohort 1

- [REDACTED]
- [REDACTED]
- AE rates as compared to ISO 11979-7:2014 Annex B SPE tables
- [REDACTED]
- SSI

HMIOL Cohort 2

- [REDACTED]
- [REDACTED]
- [REDACTED]
- [REDACTED]
- [REDACTED]
- AE rates as compared to ISO 11979-7:2014 Annex B SPE tables
- [REDACTED]
- SSI (planned Optic Exchanged procedures excluded)

7.2 EFFECTIVENESS ENDPOINTS

All HMIOL Eyes Cohort:

- Percent of eyes with post-operative BCDVA 20/40 or better by study Visit
- Percent of eyes that achieve MRSE of ± 0.50 D of target by study visit
- Percent of eyes that achieve MRSE of ± 1.00 D of target by study visit
- BCDVA by study visit
- UCDVA by study visit
- mBCDVA (with glare) by study visit

HMIOL Cohort 1

- Percent of eyes with post-operative BCDVA 20/40 or better by study visit
- Percent of eyes that achieve MRSE of ± 0.50 D of target by study visit
- Percent of eyes that achieve MRSE of ± 1.00 D of target by study visit
- BCDVA by study visit
- UCDVA by study visit

HMIOL Cohort 2

- Percent of eyes with post-operative BCDVA 20/40 or better by study visit
- Percent of eyes that achieve UCDVA by post-optic exchange study visit
 - 20/20 or better
 - 20/25 or better
 - 20/32 or better
 - 20/40 or better
 - Worse than 20/40
- Percent of eyes that achieve MRSE of ± 0.50 D of optic exchange target by post-optic exchange study visit
- Percent of eyes that achieve MRSE of ± 1.00 D of optic exchange target by post-optic exchange study visit
- BCDVA by study visit
- UCDVA by study visit

[REDACTED]

- [REDACTED]
- [REDACTED]
- [REDACTED]
- [REDACTED]
- [REDACTED]
- [REDACTED]
- [REDACTED]
- [REDACTED]
- [REDACTED]
- [REDACTED]
- [REDACTED]

8.0 STATISTICAL METHODS

This is a feasibility study to evaluate the safety and effectiveness of HMIOL in subjects with primary cataract surgery and subjects with HMIOL optic exchange. In general, the analyses will be provided based on available data. The mean, standard deviation, minimum, and maximum will be prepared for the continuous clinical parameters, and counts and percentages will be presented for the categorical outcomes.

8.1 SAMPLE SIZE CALCULATION

The sample size of this feasibility study is first calculated based on ISO 11979-7:2014 (E) to evaluate the proportion of HMIOL-implanted eyes with BCDVA of 0.3 logMAR or better for All HMIOL Cohort (post optic exchange for HMIOL Cohort 2). The statistical hypotheses for the effectiveness are H0: $p \geq 0.925$ and Ha: $p < 0.925$, where p is the proportion of HMIOL-implanted eye with BCDVA of 0.3 logMAR. The sample size based on the binomial distribution with a one-side significance level of 0.05 and a power at a true p of 0.85. The table below summarizes the sample sizes and the corresponding statistical power. For this feasibility study, a sample size of at least 100 subjects will provide a statistical power of at least 75% to accept the alternative hypothesis of $p < 0.925$ if the true p is 0.85.

Sample Size	Statistical Power
100	0.753
110	0.785
120	0.813
130	0.837
140	0.858
150	0.876
160	0.891
170	0.905

It should be noted that this is a feasibility study. All the analyses are to evaluate the effectiveness and safety of the HMIOL for the future confirmatory study. No adjustment is performed for the multiplicity.

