
Sample Size
	
The sample size of this feasibility study is first calculated based on ISO 11979-7:2014 (E) to evaluate the proportion of HMIOL-implanted eyes with BCDVA of 0.3 logMAR of better for all HMIOL Cohort (post optic exchange for HMIOL Cohort 2). The statistical hypotheses for the effectiveness are $H_0: p \geq 0.925$ and $H_a: p < 0.925$, where p is the proportion of HMIOL-implanted eye with BCDVA of 0.3 logMAR. Based on the binomial distribution with a one-side significance level of 0.05 and a true p of 0.85, a sample size of 100 eyes will provide a statistical power of about 75%; while a sample size of 200 eyes will provide a statistical power of about 95%. Therefore, a sample size of 100 to 200 eyes implanted with HMIOL will be required for the study. For any adverse events that are not observed during the study, the one-sided upper 95% confidence limit of the adverse event rate is 0.0362 if the sample size is 100 eyes. The one-sided upper 95% confidence limit of the adverse event rate is 0.0183 if the sample size is 200 eyes. Therefore, a sample size of 100 to 200 deems to be sufficient for evaluating the safety and effectiveness of HMIOL for this feasibility study.
 
[REDACTED] [REDACTED] [REDACTED] [REDACTED]

	
[REDACTED]
 
The goal will be to enroll up to 200 subjects. However, after the first 25 subjects have reached the 3 month time point (and every 25 subjects thereafter), subject accountability and the rate of optic exchanges will be evaluated, and the enrollment goal will be reevaluated with respect to achieving the necessary sample size.
 
It should be noted that this is a feasibility study. All the analyses are to evaluate the effectiveness and safety of the HMIOL for the future confirmatory study. No adjustment is performed for the multiplicity.

--	--

[REDACTED]

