4.7.1 EARLY STUDY TERMINATION

ClarVista has the right to terminate this study at any time. Reasons for terminating the study may include, but are not limited to, the following:

- The incidence or severity of adverse events in this or any ongoing studies involving the same technology (if applicable), indicates a potential health hazard to subjects
- Subject enrollment is unsatisfactory
- Data recording is inaccurate or incomplete.
- A minimum of 105 subjects has been enrolled in the study *and* a minimum of 44 optic exchanges has taken place.

In the event of premature study termination, appropriate notification will be given to the Investigators, IRB / ECs, and regulatory bodies as applicable. In addition, ClarVista (or designee) will instruct all Investigators to discontinue dispensing study materials or treatments, will ensure all subjects complete appropriate follow-up, and will arrange study closeout visits at each site as appropriate.

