8.3 STATISTICAL METHODS

The data analyses will be based on the analysis populations described above. No imputation for missing data will be performed. The statistical summaries will be prepared for HMIOL Cohort 1, HMIOL Cohort 2, and HMIOL eye Cohort (Cohort 1 + Cohort 2). For some selected outcomes, the summaries will be prepared for the fellow eye cohort.

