8.3.2.1 BCDVA

The LogMAR will be derived for BCDVA. The descriptive statistics for continuous variables will be used to summarize LogMAR BCDVA at each visit based on the implanted-eye population for the three different lens cohorts (HMIOL Cohort 1, HMIOL Cohort 2, and Fellow-eye Cohort). The data at preoperative and 3-month post-primary-surgery will also be summarized for the HMIOL-eye cohort.

Additionally, the number and percentage of eyes reaching BCDVA 20/40 or better at each visit will be prepared for Cohort 1, Cohort 2, and the Fellow-eye Cohort. The one-sided upper 95% confidence limit of the proportion of HMIOL eyes with 20/40 or better will be calculated based on the binomial distribution and compared to a target of 0.925. If the confidence limit is > 0.925 , then the null hypothesis of $p \geq 0.925$ will not be rejected.

The analyses will be repeated based on the Per Protocol Population and the Best-case Population.

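### Protocol 8.1 says 100 or more gives at least 75% power; by its own exact test this fails at 105, 106 and 107 evaluable eyes (72.4% at 105)

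*Protocol*

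**What the plan says.** Protocol Section 8.1 sizes the study on the proportion of implanted eyes reaching best-corrected distance acuity of 0.3 logMAR (20/40) or better. The null hypothesis is that this proportion is at least 0.925; the alternative is that it is lower. The calculation is "based on the binomial distribution with a one-side significance level of 0.05 and a power at a true p of 0.85". Power is tabulated at 100, 110 and so on to 170, rising from 0.753 to 0.905. The text concludes that "a sample size of at least 100 subjects will provide a statistical power of at least 75" per cent.

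The Sample Size entry of the synopsis is narrower. It says that "a sample size of 100 eyes will provide a statistical power of about 75" per cent, gives about 95% at 200 eyes, and states that "a sample size of 100 to 200 eyes implanted with HMIOL will be required for the study".

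Section 8.3.2.1 sets the decision rule: a one-sided upper 95% binomial confidence limit is compared with 0.925, and the null stands if the limit lies above that value.

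Section 4.7.1 lists reasons for which the sponsor may stop the study early. One is a joint condition: "A minimum of 105 subjects has been enrolled in the study", together with at least 44 optic exchanges.

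**The concern.** The sentence in 8.1 covers every sample size from 100 upward, but it rests on eight values spaced 10 apart. Exact binomial power does not rise steadily with sample size. It climbs while the rejection limit moves up with each added eye, and drops when the limit stays where it is. A table in steps of 10 can show a smooth rise and miss the drops.

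The direction matters because of how the hypotheses are set. Rejecting the null is the unfavourable result, and failing to reject is the favourable one. Power here is the chance of flagging a lens whose true rate is only 0.85, so any shortfall makes it more likely that such a lens passes. This is also the hypothesis on which 8.1 first bases the sample size, and 105, a number the protocol itself uses in 4.7.1, is one of the sizes at which the claim fails.

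**Working it through.** **Inputs.** Null proportion 0.925, true proportion 0.85, one-sided level 0.05, binomial distribution (all Section 8.1); decision by one-sided upper 95% binomial limit against 0.925 (Section 8.3.2.1).

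**Formulas.** Let X be the number of eyes at 20/40 or better out of n.

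- Rejection limit: c = the largest value with P(X ≤ c | n, 0.925) ≤ 0.05.
- Attained alpha = P(X ≤ c | n, 0.925).
- Power = P(X ≤ c | n, 0.85).

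**Step 1: reproduce the plan's table.**

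| n | c | attained alpha | power | protocol |
|---|---|---|---|---|
| 100 | 87 | 0.0364 | 0.7527 | 0.753 |
| 110 | 96 | 0.0360 | 0.7852 | 0.785 |
| 120 | 105 | 0.0353 | 0.8131 | 0.813 |
| 130 | 114 | 0.0345 | 0.8371 | 0.837 |
| 140 | 123 | 0.0336 | 0.8578 | 0.858 |
| 150 | 132 | 0.0327 | 0.8757 | 0.876 |
| 160 | 141 | 0.0316 | 0.8912 | 0.891 |
| 170 | 150 | 0.0306 | 0.9047 | 0.905 |

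All eight rows agree to three decimals. At n = 200 power is 0.9585, which fits the synopsis's approximate 95%. Other methods do not give 0.753 at n = 100: normal approximation 0.812 (0.772 with continuity correction), Wald 0.676, arcsine 0.777, exact test at one-sided 0.025 0.653. The plan therefore used the exact test at one-sided 0.05.

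**Step 2: fill in the sizes between 100 and 110.**

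| n | c | attained alpha | power |
|---|---|---|---|
| 100 | 87 | 0.0364 | 0.7527 |
| 101 | 88 | 0.0390 | 0.7653 |
| 102 | 89 | 0.0418 | 0.7774 |
| 103 | 90 | 0.0447 | 0.7891 |
| 104 | 91 | 0.0477 | 0.8003 |
| **105** | **91** | **0.0254** | **0.7239** |
| **106** | **92** | **0.0273** | **0.7370** |
| **107** | **93** | **0.0293** | **0.7497** |
| 108 | 94 | 0.0314 | 0.7619 |
| 109 | 95 | 0.0336 | 0.7738 |
| 110 | 96 | 0.0360 | 0.7852 |

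From 104 to 105 the limit stays at 91 successes, attained alpha falls from 4.8% to 2.5%, and power falls by 80.0 − 72.4 = 7.6 points. The confidence-limit rule gives the same cut-off. At n = 105 the one-sided upper 95% Clopper-Pearson limit is 0.9176 for 91 successes (reject) and 0.9252 for 92 (do not reject).

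**Step 3: the rest of the range.** Later drops occur (for example 0.8363 at 115 to 0.7706 at 116), but power is at least 0.75 at every n from 108 to 200. The lowest value anywhere from 100 to 200 is 0.7239, at 105.

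**Step 4: size of the shortfall.** 75 − 72.39 = 2.6 points at 105; 75 − 73.70 = 1.3 at 106; 75 − 74.97 = 0.03 at 107. At 105 a lens with a true rate of 0.85 passes with probability 1 − 0.7239 = 27.6%, against the 25% at most that 8.1 implies.

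**Step 5: from 105 enrolled to eyes analysed.** No dropout rate is visible, so the losses below are assumptions.

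| eyes lost of 105 | evaluable | power |
|---|---|---|
| 0 | 105 | 72.4% |
| 1 to 5 | 104 to 100 | 80.0% down to 75.3% |
| 6 to 10 | 99 to 95 | 74.0% down to 68.3% |

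**The case against.** The strongest reply is that this is ordinary binomial discreteness. Three of the 101 sizes from 100 to 200 are affected, one of them by 0.03 points. The SAP (Section 4) says that formal tests in this study are not meant to give definitive conclusions for regulatory approval. No decision, sample size or analysis changes. All of that stands and sets the severity, but it does not make the sentence in 8.1 true.

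A reader might infer more than the documents support, in four ways.

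- **That 105 is the protocol's only minimum, or its closing sample size.** It is neither. Section 8.1 and the synopsis both name 100, where power is 75.3% as stated. The 105 in 4.7.1 is half of a joint condition, in a list of reasons for which the sponsor may stop; the goal is up to 200 subjects, with enrolment re-evaluated every 25.
- **That the test would be run on 105 eyes.** Section 4.7.1 counts enrolled subjects. Enrolment precedes surgery (3.3.1), subjects not implanted are discontinued (4.5), the per-protocol population is primary for effectiveness (8.2.3), and "No imputation for missing data will be performed" (8.3). The 72.4% applies only if every enrolled eye is analysed.
- **That attrition can only make things worse.** Losing 1 to 5 of 105 eyes restores at least 75%. Losing 6 to 10 takes power below 75%, but at sizes under 100, about which 8.1 claims nothing.
- **That the synopsis is also wrong.** Its approximate figures at 100 and 200 eyes match the exact 75.3% and 95.85%.

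The basis for 105 and 44 may also be explained where it cannot be read. The synopsis's sample-size text has redacted blocks, and the SAP's contents list a Sample Size section whose text is not in the available copy. Nor is the lack of rejection limits and attained alpha in the table an error; printing them would simply be good practice.

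**Conclusion.** The general power statement in 8.1 is false at 105, 106 and 107 evaluable eyes under the plan's own test, with a largest shortfall of 2.6 points. The table is right. The result needs no assumption beyond the inputs in 8.1, since the exact method is confirmed by matching all eight rows. Its link to the 105 in 4.7.1 does need one: how many of 105 enrolled eyes would be evaluable, which the visible text does not say. The documents do not support calling the study underpowered at its planned size. Severity is minor.

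**What to change.** Replace the sentence in 8.1 with a statement that exact power is at least 75% at 100 to 104 and at 108 or more evaluable eyes, and at least 72% for any size from 100 to 200. Count evaluable eyes rather than subjects. In the same place, give the power at the 105 floor of 4.7.1: 72.4% if all 105 eyes are evaluable, with the values for plausible losses beside it. Optionally, add the rejection limit and attained alpha to each row of the table. Leave the synopsis figures at 100 and 200 as they are.

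The cost is a change of wording and a slightly less favourable stated figure. No extra patients and no change to the design or analysis are involved.
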